1.0 TRIAL SUMMARY

Abbreviated Title	Phase II study of pembrolizumab in Subjects with Advanced Gastric or Gastroesophageal Junction Adenocarcinoma who Progressed after First-Line Therapy with Platinum and Fluoropyrimidine: integration of molecular subtypes through integrative genomic analysis.
Trial Phase	II
Clinical Indication	Advanced Gastric or Gastroesophageal Junction (GEJ) Adenocarcinoma
Trial Type	Interventional
Type of control	One arm
Route of administration	Intravenous
Trial Blinding	Open-label
Treatment Groups	Pembrolizumab (MK-3475) 200 mg every 3 weeks (Q3W)
Number of trial subjects	Approximately up to 40 subjects will be enrolled.
Estimated enrollment period	12 months
Estimated duration of trial	
Investigator estimates that the trial will require approximately 24 months from the time the first subject signs the informed consent until last subject's last visit.
 
Estimated date of first subject enrolled : Q3 2015
 
Estimated date of last subject completed: Q3 2017

Duration of Participation	
Each subject will participate in the trial from the time the subject signs the Informed Consent Form (ICF) through the final contact. After a screening phase of up to 28 days, eligible subjects will receive treatment beginning on Day 1 of each 3-week dosing cycle for pembrolizumab. Treatment with pembrolizumab will continue until documented disease progression, unacceptable adverse event(s), intercurrent illness that prevents further administration of treatment, Investigator's decision to withdraw the subject, subject withdraws consent, pregnancy of the subject, noncompliance with trial treatment or procedure requirements, subject receives 24 months of pembrolizumab, or administrative reasons requiring cessation of treatment. After the end of treatment, each subject will be followed for 30 days for adverse event monitoring (serious adverse events and events of clinical interest will be collected for 90 days after the end of treatment or 30 days after the end of treatment if the subject initiates new anticancer therapy, whichever is earlier).
 
Subjects who discontinue after 24months of therapy for reasons other than disease progression or intolerance or who discontinue after attaining a CR may be eligible for up to one year of retreatment after they have experienced radiographic disease progression.

2.0 TITLE OF THE STUDY

Phase II study of pembrolizumab in Subjects with Advanced Gastric or Gastroesophageal Junction Adenocarcinoma who Progressed after First-Line Therapy with Platinum and Fluoropyrimidine: integration of molecular subtypes through integrative genomic analysis.

5.0 TRIAL DESIGN

5.1 Trial Design

This is a single-arm, single-center, open-label trial of pembrolizumab (MK-3475) in subjects with advanced gastric or gastroesophageal junction (GEJ) adenocarcinoma who have progressed after failure of any combination chemotherapy containing a platinum and a fluoropyrimidine agent.

Approximately 40 subjects will be enrollment to evaluate the efficacy and safety of pembrolizumab.

Enrollment will begin with all subjects without regard for PD-L1 expression status.

An evaluable specimen for PD-L1 status must be available and confirmed prior to enrollment.

All study subjects will be evaluated every 6 weeks (+/- 7 days) following the date of IP drug administration for the first six months and every 12 weeks (+/- 7 days) thereafter until progression of disease is documented with radiologic imaging (computed tomography or magnetic resonance imaging).

The primary efficacy endpoint is ORR (objective response rate) per mRECIST.

If a subject has progression of disease by mRECIST, it is recommended that the subject be discontinued from the study treatment unless, in the Investigator's opinion, the subject is deriving benefit from treatment.

Clinically stable subjects may continue to receive trial therapy at the discretion of the Investigator. If a repeat scan confirms progression of disease and the subject remains clinically stable, the subject may continue treatment .

Adverse events will be monitored throughout the trial and graded in severity according to the guidelines outlined in the NCI Common Terminology Criteria for Adverse Events (CTCAE) version 4.0.

[figure not shown]
Except as noted above, treatment with pembrolizumab will continue until documented disease progression, unacceptable adverse event(s), intercurrent illness that prevents further administration of treatment, Investigator's decision to withdraw the subject, subject withdraws consent, pregnancy of the subject, noncompliance with trial treatment or procedure requirements, completion of 24 months of pembrolizumab, or administrative reasons requiring the cessation of treatment.

After the end of treatment, each subject will be followed for 30 days for adverse event monitoring (serious adverse events and events of clinical interest will be collected for 90 days after the end of treatment or 30 days after the end of treatment if the subject initiates new anticancer therapy, whichever is earlier). Subjects who discontinue treatment for reasons other than disease progression will have post-treatment follow-up for disease status until disease progression, initiating a non-study cancer treatment, withdrawing consent, or becoming lost to follow-up. All subjects will be followed by telephone contact for overall survival until death, withdrawal of consent or the end of the study, whichever comes first.

This study will be conducted in conformance with Good Clinical Practices.

Specific procedures to be performed during the trial, as well as their prescribed times and associated visit windows, are outlined in the Trial Flow Chart. Details of each procedure are provided in Trial Procedures.

5.2 Trial Diagram

6.0 OBJECTIVE(S) & HYPOTHESIS(ES)

6.1 Primary efficacy Objective(s) & Hypothesis(es)

Objective: To evaluate RR per mRECIST in advanced gastric or GEJ adenocarcinoma who have progressed on one previous line of therapy, when treated with pembrolizumab

Hypothesis: Pembrolizumab increases RR per mRECIST with advanced gastric or GEJ adenocarcinoma who have progressed on 1 previous line of therapy

6.2 Primary genomic Objective(s) & Hypothesis(es)

(1) Objective: Integrative genomic analysis to identify predictive markers (i.e. immune signatures) and analyze the response rate according to molecular signatures identified through the ACRG effort.; Categorization: 1) mesenchymal, 2) MSI, 3) MSS-TP 53 intact, 4) MSS- TP53 mutation

Hypothesis: Association of response with tumor histology

Association of response with molecular signatures at baseline

Activation of immune pathways post treatment and association with response

Be good response to Pembrolizumab in MSS-MSI molecular and high-mutational burden type

6.3 Exploratory Objective

- (1) **Objective:** Genomic analysis: Whole Exome Sequencing at baseline, RNA-seq pre and post (WES will be performed at SMC and analyzed together with the BI team at MERCK MSD (GpGx CSB and PGx Groups, Drs. [name], [name], [name], [name] and [name]) and SMC (Genome Center and Molecular Pathology).
- (2) As an exploratory analysis, we will isolate T cells using FACS sorting and sequence these cells. In addition, in order to identify the relationship between neoantigen drivers

like infection and response to pembrolizumab, we will prospectively collect serum antigens from blood at baseline.

7.0 BACKGROUND & RATIONALE

7.1 Background

Refer to the Investigator's Brochure (IB)/approved labeling for detailed background information on MK-3475.

7.1.1 Pharmaceutical and Therapeutic Background

The importance of intact immune surveillance in controlling outgrowth of neoplastic transformation has been known for decades. Accumulating evidence shows a correlation between tumor-infiltrating lymphocytes (TILs) in cancer tissue and favorable prognosis in various malignancies. In particular, the presence of CD8+ T-cells and the ratio of CD8+ effector T-cells / FoxP3+ regulatory T-cells seems to correlate with improved prognosis and long-term survival in many solid tumors.

The PD-1 receptor-ligand interaction is a major pathway hijacked by tumors to suppress immune control. The normal function of PD-1, expressed on the cell surface of activated T-cells under healthy conditions, is to down-modulate unwanted or excessive immune responses, including autoimmune reactions. PD-1 (encoded by the gene Pdcd1) is an Ig superfamily member related to CD28 and CTLA-4 which has been shown to negatively regulate antigen receptor signaling upon engagement of its ligands (PD-L1 and/or PD-L2). The structure of murine PD-1 has been resolved. PD-1 and family members are type I transmembrane glycoproteins containing an Ig Variable-type (V-type) domain responsible for ligand binding and a cytoplasmic tail which is responsible for the binding of signaling molecules. The cytoplasmic tail of PD-1 contains 2 tyrosine-based signaling motifs, an immunoreceptor tyrosine-based inhibition motif (ITIM) and an immunoreceptor tyrosine-based switch motif (ITSM). Following T-cell stimulation, PD-1 recruits the tyrosine phosphatases SHP-1 and SHP-2 to the ITSM motif within its cytoplasmic tail, leading to the dephosphorylation of effector molecules such as CD3 ζ , PKC θ and ZAP70 which are involved in the CD3 T-cell signaling cascade. The mechanism by which PD-1 down modulates T-cell responses is similar to, but distinct from that of CTLA-4 as both molecules regulate an overlapping set of signaling proteins. PD-1 was shown to be expressed on activated lymphocytes including peripheral CD4+ and CD8+ T-cells, B-cells, Tregs and Natural Killer cells. Expression has also been shown during thymic development on CD4-CD8- (double negative) T-cells as well as subsets of macrophages and dendritic cells. The ligands for PD-1 (PD-L1 and PD-L2) are constitutively expressed or can be induced in a variety of cell types, including non-hematopoietic tissues as well as in various tumors. Both ligands are type I transmembrane receptors containing both IgV- and IgC-like domains in the extracellular region and contain short cytoplasmic regions with no known signaling motifs. Binding of either PD-1 ligand to PD-1 inhibits T-cell activation triggered through the T-cell receptor. PD-L1 is expressed at low levels on various non-hematopoietic tissues, most notably on vascular endothelium, whereas PD-L2 protein is only detectably expressed on

antigen-presenting cells found in lymphoid tissue or chronic inflammatory environments. PD-L2 is thought to control immune T-cell activation in lymphoid organs, whereas PD-L1 serves to dampen unwarranted T-cell function in peripheral tissues. Although healthy organs express little (if any) PD-L1, a variety of cancers were demonstrated to express abundant levels of this T-cell inhibitor. PD-1 has been suggested to regulate tumor-specific T-cell expansion in subjects with melanoma (MEL). In gastric cancer PD-L1 and PD-L2 overexpression have recently been associated with EBV-positive tumors. This suggests that the PD-1/PD-L1 pathway plays a critical role in tumor immune evasion and should be considered as an attractive target for therapeutic intervention.

Pembrolizumab is a potent and highly selective humanized monoclonal antibody (mAb) of the IgG4/kappa isotype designed to directly block the interaction between PD-1 and its ligands, PD-L1 and PD-L2. Keytruda™ (pembrolizumab) has recently been approved in the United States for the treatment of patients with unresectable or metastatic melanoma and disease progression following ipilimumab and, if BRAF V600 mutation positive, a BRAF inhibitor.

7.1.2 Preclinical and Clinical Trial Data

Refer to the Investigator's Brochure for Preclinical and Clinical data.

The preliminary data showed a Not significant correlation between PD-L-1 expression and ORR (P=0.071).

Given the mutual association of tumor genetic markers, gene expression and potential markers of response to immune therapy identified through the collaborative work between SMC and MERCK MSD and Lilly, we plan to perform a phase II study with integrative genomic analysis (whole exome and RNA sequencing) in pre and post biopsy specimens to better define those GCs who may benefit from pembro.

7.2.2 Rationale for Dose Selection/Regimen/Modification

An open-label Phase I trial (Protocol 001) is being conducted to evaluate the safety and clinical activity of single agent MK-3475. The dose escalation portion of this trial evaluated three dose levels, 1 mg/kg, 3 mg/kg, and 10 mg/kg, administered every 2 weeks (Q2W) in subjects with advanced solid tumors. All three dose levels were well tolerated and no dose-limiting toxicities were observed. This first in human study of MK-3475 showed evidence of target engagement and objective evidence of tumor size reduction at all dose levels (1 mg/kg, 3 mg/kg and 10 mg/kg Q2W). No MTD has been identified to date. 10.0 mg/kg Q2W, the highest dose tested in PN001, will be the dose and schedule utilized in Cohorts A, B, C and D of this protocol to test for initial tumor activity. Recent data from other clinical studies within the MK-3475 program has shown that a lower dose of MK-3475 and a less frequent schedule may be sufficient for target engagement and clinical activity.

PK data analysis of MK-3475 administered Q2W and Q3W showed slow systemic clearance, limited volume of distribution, and a long half-life (refer to IB). Pharmacodynamic data (IL-2 release assay) suggested that peripheral target engagement is durable (>21 days). This early PK and pharmacodynamic data provides scientific rationale for testing a Q2W and Q3W dosing schedule.

A population pharmacokinetic analysis has been performed using serum concentration time data from 476 patients. Within the resulting population PK model, clearance and volume parameters of MK-3475 were found to be dependent on body weight. The relationship between clearance and body weight, with an allometric exponent of 0.59, is within the range observed for other antibodies and would support both body weight normalized dosing or a fixed dose across all body weights. MK-3475 has been found to have a wide therapeutic range based on the melanoma indication. The differences in exposure for a 200 mg fixed

dose regimen relative to a 2 mg/kg Q3W body weight based regimen are anticipated to remain well within the established exposure margins of 0.5 – 5.0 for MK-3475 in the melanoma indication. The exposure margins are based on the notion of similar efficacy and safety in melanoma at 10 mg/kg Q3W vs. the proposed dose regimen of 2 mg/kg Q3W (i.e. 5-fold higher dose and exposure). The population PK evaluation revealed that there was no significant impact of tumor burden on exposure. In addition, exposure was similar between the NSCLC and melanoma indications. Therefore, there are no anticipated changes in exposure between different indication settings.

The rationale for further exploration of 2 mg/kg and comparable doses of pembrolizumab in solid tumors is based on: 1) similar efficacy and safety of pembrolizumab when dosed at either 2 mg/kg or 10 mg/kg Q3W in melanoma patients, 2) the flat exposure-response relationships of pembrolizumab for both efficacy and safety in the dose ranges of 2 mg/kg Q3W to 10 mg/kg Q3W, 3) the lack of effect of tumor burden or indication on distribution behavior of pembrolizumab (as assessed by the population PK model) and 4) the assumption that the dynamics of pembrolizumab target engagement will not vary meaningfully with tumor type.

The choice of the 200 mg Q3W as an appropriate dose for the switch to fixed dosing is based on simulations performed using the population PK model of pembrolizumab showing that the fixed dose of 200 mg every 3 weeks will provide exposures that 1) are optimally consistent with those obtained with the 2 mg/kg dose every 3 weeks, 2) will maintain individual patient exposures in the exposure range established in melanoma as associated with maximal efficacy response and 3) will maintain individual patients exposure in the exposure range established in melanoma that are well tolerated and safe.

A fixed dose regimen will simplify the dosing regimen to be more convenient for physicians and to reduce potential for dosing errors. A fixed dosing scheme will also reduce complexity in the logistical chain at treatment facilities and reduce wastage.

7.2.3 Rationale for Endpoints

7.2.3.1 Efficacy Endpoints

mRECIST will be adapted to account for the unique tumor response profile seen with immunotherapies such as pembrolizumab. Immunotherapeutic agents such as pembrolizumab may produce antitumor effects by potentiating endogenous cancer-specific immune responses which may be functionally anergic. The response patterns seen with such an approach may extend beyond the typical time course of responses seen with cytotoxic agents, and can manifest a clinical response after an initial increase in tumor burden or even the appearance of new lesions.

When feasible, subjects within the pembrolizumab arm should not be discontinued until progression is confirmed. This allowance to continue treatment despite initial radiologic progression takes into account the observation that some subjects can have a transient tumor

flare in the first few months after the start of immunotherapy, but with subsequent disease response.

7.2.3.2 Biomarker Research

We will conduct Biomarker Research on specimens collected during this clinical trial. This research may include genetic analyses (DNA), gene expression profiling (RNA), proteomics, metabolomics (serum, plasma) and/or the measurement of other analytes.

Genomic analysis: Whole Exome Sequencing at baseline, RNA-seq pre and post (Whole Exome Sequencing will be performed at SMC and analyzed together with the BI team at MERCK MSD (GpGx CSB and PGx Groups, Drs. [name], [name], [name], [name] and [name]) and SMC (Genome Center and Molecular Pathology).

Asian Cancer Research Group (ACRG) cohort with operable gastric cancer subjects found a strong association between high expression of PD-L1 and either MSI/hypermutation or EBV infection. In addition, the above subtypes exhibited differential prognosis on overall survival, with the EBV infection subtype and the MSI subtype displaying the best prognosis among all the subtypes.

The objective of collecting specimens for Biomarker Research is to explore and identify biomarkers that inform the scientific understanding of diseases and/or their therapeutic treatments. Integrative genomic analysis (i.e. gene signature, MSH, etc.) measured may be a predictive biomarker for patients who receive pembrolizumab treatment.

As an exploratory analysis, we will isolate T cells using FACS sorting and sequence these cells. In addition, in order to identify the relationship between neoantigen drivers like infection and response to pembrolizumab, we will prospectively collect serum antigens from blood at baseline.

8.0 METHODOLOGY

8.1 Entry Criteria

8.1.1 Diagnosis/Condition for Entry into the Trial

8.1.2 Subject Inclusion Criteria

In order to be eligible for participation in this trial, the subject must:

1. Be willing and able to provide written informed consent/assent for the trial. The subject may also provide consent for Biomedical Research. However, the subject may participate in the main trial without participating in Biomedical Research.
2. Be ≥ 19 years of age on day of signing informed consent (or acceptable age according to local regulations, whichever is older).
3. Have histologically or cytologically-confirmed diagnosis of gastric or GEJ

adenocarcinoma.

4. Have metastatic disease or locally advanced, unresectable disease.
5. Has experienced documented objective radiographic or clinical disease progression during or after first-line therapy containing any platinum/fluoropyrimidine doublet.
 - a. To be considered as second-line, the subject needs to have the documentation of disease progression on first-line treatment. The disease progression can be confirmed by CT scan or by clinical evidence (such as cytology report from newly developed ascites and plural effusion).
 - b. Any new or worsening malignant effusion (documented by ultrasound) may be confirmed by pathologic criteria (histology and/or cytology) if appropriate.
 - c. A subject experiencing clinical disease progression during or within 6 months following the last dose of adjuvant therapy will be eligible for enrollment provided they received a platinum/fluoropyrimidine doublet as required.
 - d. To be eligible, the subject is required to have received at least one dose of platinum and fluoropyrimidine therapy.
The dose reduction and discontinuation of one of these drugs, switching to/adding new drugs on the first-line treatment is allowed; however, the documentation of disease progression on/after the first-line treatment is required. Therefore, subjects with discontinuation due to adverse events on first-line treatment prior to disease progression are not eligible until disease progression is confirmed by documentation.
6. Have measurable disease based on mRECIST as determined by investigator. Tumor lesions situated in a previously irradiated area are considered measurable if progression has been demonstrated in such lesions.
 - a. Note: The exact same image acquisition and processing parameters should be used throughout the study.
7. Be willing to provide fresh tissue for biomarker analysis, and, based on the adequacy of the tissue sample quality for assessment of biomarker status. Repeat samples may be required if adequate tissue is not provided. Newly obtained endoscopic biopsy specimens are preferred to archived samples and formalin-fixed, paraffin-embedded (FFPE) block specimens are preferred to slides.
 - a. *Newly-obtained is defined as a specimen obtained up to 6 weeks (42 days) prior to initiation of treatment on Day 1. Subjects for whom newly-obtained samples cannot be provided (e.g. inaccessible or subject safety concern) may submit an archived specimen.*
 - b. *Collection of an archived tissue sample will also be requested (where available) to support evaluation of the clinical utility of biomarker assessment*

in newly obtained vs. archived tissue samples; however, a subject will not be precluded from participating in the study if an archived tissue sample is not available for collection or is otherwise insufficient for analysis.

8. Have a performance status of 0 or 1 on the ECOG Performance Scale.
9. Demonstrate adequate organ function as defined in Table 1, all screening labs should be performed within 10 days of treatment initiation.

Table 1 Adequate Organ Function Laboratory Values

System	Laboratory Value
Hematological	
Absolute neutrophil count (ANC)	$\geq 1,500 / \text{mcL}$
Platelets	$\geq 100,000 / \text{mcL}$
Hemoglobin	$\geq 9 \text{ g/dL}$ or $\geq 5.6 \text{ mmol/L}$ without transfusion or EPO dependency (within 7 days of assessment)
Renal	
Serum creatinine OR Measured or calculated ^a creatinine clearance (GFR can also be used in place of creatinine or CrCl)	$\leq 1.5 \times$ upper limit of normal (ULN) OR $\geq 60 \text{ mL/min}$ for subject with creatinine levels $> 1.5 \times$ institutional ULN
Hepatic	
Serum total bilirubin	$\leq 1.5 \times$ ULN OR Direct bilirubin \leq ULN for subjects with total bilirubin levels $> 1.5 \text{ ULN}$
AST (SGOT) and ALT (SGPT)	$\leq 2.5 \times$ ULN OR $\leq 5 \times$ ULN for subjects with liver metastases
Albumin	$\geq 2.5 \text{ mg/dL}$
Coagulation	
International Normalized Ratio (INR) or Prothrombin Time (PT)	$\leq 1.5 \times$ ULN unless subject is receiving anticoagulant therapy as long as PT or PTT is within therapeutic range of intended use of anticoagulants
Activated Partial Thromboplastin Time (aPTT)	$\leq 1.5 \times$ ULN unless subject is receiving anticoagulant therapy as long as PT or PTT is within therapeutic range of intended use of anticoagulants

^aCreatinine clearance should be calculated per institutional standard.

10. Female subject of childbearing potential should have a negative urine or serum pregnancy within 72 hours prior to receiving the first dose of study medication. If the urine test is positive or cannot be confirmed as negative, a serum pregnancy test will be required.
11. Female subjects of childbearing potential should be willing to use 2 methods of birth control or be surgically sterile, or abstain from heterosexual activity for the course of the study through 120 days after the last dose of study medication (Reference Section 5.7.2). Subjects of childbearing potential are those who have not been surgically sterilized or have not been free from menses for > 1 year.

12. Male subjects should agree to use an adequate method of contraception starting with the first dose of study therapy through 120 days after the last dose of study therapy.

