10.1.3 Laboratory Procedures/Assessments

Details regarding specific laboratory procedures/assessments to be performed in this trial are provided belowLaboratory Safety Evaluations (Hematology, Chemistry and Urinalysis)

Laboratory tests for hematology, chemistry, urinalysis, and others are specified in Table 5.

Table 5 Laboratory Tests

Hematology	Chemistry	Urinalysis	Other
Hematocrit	Albumin	Blood	Serum β -human chorionic gonadotropin†
Hemoglobin	Alkaline phosphatase	Glucose	(β -hCG)†
Platelet count	Alanine aminotransferase (ALT)	Protein	PT (INR)
WBC (total and differential)	Aspartate aminotransferase (AST)	Specific gravity	aPTT
Red Blood Cell Count	Lactate dehydrogenase (LDH)	Microscopic exam (If abnormal)	Total triiodothyronine (T3)
Absolute Neutrophil Count	Uric Acid	results are noted	Free tyroxine (T4)
Absolute Lymphocyte Count	Calcium	Urine pregnancy test †	Thyroid stimulating hormone (TSH)
	Chloride		
	Glucose		Blood for correlative studies
	Phosphorus		
	Potassium		
	Sodium		
	Magnesium		
	Total Bilirubin		
	Direct Bilirubin (If total bilirubin is elevated above the upper limit of normal)		
	Total protein		
	Blood Urea Nitrogen		

† Perform on women of childbearing potential only. If urine pregnancy results cannot be confirmed as negative, a serum pregnancy test will be required.

Laboratory tests for screening or entry into the Second Course Phase should be performed within 10 days prior to the first dose of treatment. After Cycle 1, pre-dose laboratory procedures can be conducted up to 72 hours prior to dosing. Results must be reviewed by the investigator or qualified designee and found to be acceptable prior to each dose of trial treatment.

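### The albumin entry limit in Table 1 is printed in mg/dL, so the row excludes nobody as written

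*Combined protocol and SAP*

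**What the plan says.** Section 8.1.2, item 9, requires each subject to "Demonstrate adequate organ function as defined in Table 1, all screening labs should be performed within 10 days of treatment initiation". Table 1 is therefore part of the eligibility rule.

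In the hepatic block of Table 1 the albumin row reads "Albumin $\geq 2.5 \text{ mg/dL". The other two hepatic rows are multiples of the upper limit of normal: total bilirubin, with a direct-bilirubin alternative, and "AST (SGOT) and ALT (SGPT) $\leq 2.5 \times$ ULN OR $\leq 5 \times$ ULN for subjects with liver metastases". The haemoglobin row is also a mass per decilitre, and it is stated as "\geq 9 \text{ g/dL}$ or $\geq 5.6 \text{ mmol/L}$ without transfusion or EPO dependency".

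Albumin appears in one other place, the chemistry column of Table 5 (Section 10.1.3), where it is listed as a test with no unit and no reference range. Neither the exclusion criteria (Section 8.1.3) nor the screening section (Section 10.1.5.1) gives an albumin limit.

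**The concern.** The printed limit is about a thousandth of the concentrations at which serum albumin is found. A minimum set that low is met by everyone, so the row no longer separates adequate from inadequate values. Its evident purpose is to keep out patients with severely low albumin.

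Two things could follow, and neither is satisfactory.

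- **The text is applied as printed**, by hand or in a data-entry check. A patient with very low albumin then satisfies the row.
- **Staff recognise the slip and use another unit without an amendment.** The enrolled population is then not the one the protocol defines. A patient refused at, say, 2.3 g/dL (2,300 mg/dL) had met the written criterion. A patient enrolled at that value could not be recorded as a deviation.

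Section 10.1.1.3 requires every criterion to be reviewed, and Section 14.0 has the monitor check protocol compliance and verify source data. The printed text is the standard for both. Section 8.6.1 also makes retreatment after a complete response depend on the safety parameters in the entry criteria, so the same row may be consulted a second time.

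**Working it through.** The limit is a stated threshold and not a derived figure, so there is nothing of the plan's own to reproduce. The check is a unit conversion and a comparison.

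**Inputs**

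- Printed limit: 2.5 mg/dL (Table 1, hepatic block).
- Conversion: 1 g/dL = 1,000 mg/dL.
- Serum albumin in screened patients: the documents give no figure. *Assumption:* 1.0 to 5.5 g/dL, chosen to be wider than needed.

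**Step 1. Convert the limit.** 2.5 / 1,000 = 0.0025 g/dL.

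**Step 2. Compare with assumed values.** Multiple of the limit = (albumin in g/dL × 1,000) / 2.5.

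| Albumin (g/dL) | Albumin (mg/dL) | Multiple of printed limit | Meets the row? |
|---|---|---|---|
| 1.0 | 1,000 | 400 | yes |
| 1.5 | 1,500 | 600 | yes |
| 2.0 | 2,000 | 800 | yes |
| 2.5 | 2,500 | 1,000 | yes |
| 3.5 | 3,500 | 1,400 | yes |
| 5.0 | 5,000 | 2,000 | yes |
| 5.5 | 5,500 | 2,200 | yes |

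**Step 3. Share excluded.** To fail the row, a patient would need albumin below 0.0025 g/dL, which is 1/400 of the lowest value in the assumed range. The share excluded is therefore 0% whatever the distribution within that range.

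**Step 4. Is the unit a fault of text reading?** The haemoglobin row of the same table came through intact with g/dL. Its two forms also agree: taking a monomer molar mass of 16.114 kg/mol (an assumption), 9 g/dL = 90 g/L, and 90 / 16.114 = 5.59 mmol/L, against the printed 5.6. The albumin cell likewise has a clean relation sign, number and unit. A misread cannot be ruled out entirely, but nothing points to one.

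**Step 5. What else in Table 1 is affected?** Nothing. The bilirubin, AST/ALT, INR/PT and aPTT limits are multiples of the upper limit of normal and do not depend on the albumin unit.

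**The case against.** The other side accepts the printed value and the conversion, and disputes the weight.

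- **Only one row is inert.** Item 9 requires every row of Table 1, so a patient with poor hepatic function can still fail on bilirubin, transaminases or coagulation. This stands, and the point is limited to the albumin row.
- **Other provisions give some cover.** Exclusion 13 (Section 8.1.3) lets the investigator bar a subject for a laboratory abnormality. Inclusion 8 requires ECOG 0 or 1. Section 10.1.3 requires laboratory results to be reviewed and found acceptable before each dose. These lower the practical risk. Exclusion 13 and the pre-dose review are matters of judgement, however, and ECOG does not measure albumin, so none of them replaces a numeric limit.
- **The slip is obvious and the trial has one centre.** Staff would probably notice it, sites cannot diverge, and the documents contain no specification of a data-entry check. This makes literal use unlikely. It makes silent correction the likely outcome, and that is the case in which decisions cannot be audited.
- **The trial's conclusions do not move.** The response-rate definition (Section 11.1.1.1) and the sample size (Section 11.2) do not use the limit. This is true, and it is why the point is not rated higher.
- **The albumin range comes from outside the documents.** It does, and it is labelled as an assumption above. The result is the same at both ends of the range.
- **Patients already enrolled met the criterion in force.** This also stands. Any look back should describe the population and should not relabel anyone as ineligible.

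**Conclusion.** The concern holds. As printed, the albumin limit is 0.0025 g/dL, and values from 1.0 to 5.5 g/dL exceed it by a factor of 400 to 2,200. The row excludes 0% of patients in that range, and the albumin safeguard in a binding entry criterion is lost. The apparent error is a unit that is wrong by a factor of about 1,000.

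The conclusion rests on the assumed albumin range, to which it is insensitive, and on the unit having been read correctly from the document. The practical harm is probably modest. It should still be corrected, because an eligibility threshold that the protocol relies on does not work as written and nothing elsewhere repairs it.

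**What to change.** - The sponsor should confirm the intended number and unit and correct the albumin cell of Table 1. A unit of g/dL would match the haemoglobin row, but the choice of limit is the sponsor's and none is proposed here.
- Use the same unit in any case report form range check, and add it to the albumin entry in Table 5 so that the test and the limit agree.
- For patients already enrolled, compare the screening albumin on file with the corrected limit and report how many fall below it. This describes the enrolled population; those patients met the text in force when they entered.

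The cost is one table cell, a unit in Table 5, the matching data check and a short listing. Albumin is already in the chemistry panel, so no sample, visit or test is added, and the sample size and analysis stay as they are.
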